Blood Biochemistry		√		√		√	√	√	√	√	√	√	√	√	√	√		√	
Urinalysis ^c		√		√		√	√	√	√	√	√	√	√	√	√	√			

Test Items	Treatment Cycle Visit	Screening Period	C1		C2		C3	C4	C5	C6	C7	C8	C9	C10	C11	Withdrawal	28 Days after Withdrawal		Follow-up 1	Follow-up 2
			V1 (-3W)	V2	V3	V4	V5	V6	V7	V8	V9	V10	V11	V12	V13	V14	Vn	Vn+1		
Coagulation Function		✓			✓		✓	✓	✓	✓	✓	✓	✓	✓	✓					
Pregnancy Test ^d		✓																		
Stool Routine ^e		✓																		
Echocardiography ^f		✓																		
ECG ^g		✓		✓		✓	✓		✓		✓		✓		✓	✓				
Quality of Life Score ^h		✓				✓	✓		✓		✓		✓		✓	✓	✓			
Child-Pugh Score		✓																		
Imaging Evaluation-Target Lesion ⁱ		✓				✓	✓		✓		✓		✓		✓	✓			✓	
Imaging Evaluation-Non-target Lesion ⁱ		✓				✓	✓		✓		✓		✓		✓	✓			✓	
Imaging Evaluation-New Lesion ⁱ						✓	✓		✓		✓		✓		✓	✓			✓	
Inclusion and Exclusion Criteria		✓																		
Enrollment Assessment		✓																		
Drug Return and Dispensing			✓		✓	✓	✓	✓	✓	✓	✓	✓	✓	✓	✓	✓				
Blood Pressure Record			✓		✓	✓	✓	✓	✓	✓	✓	✓	✓	✓	✓	✓				
Drug Interruption Form																		✓		
Dose Modification Form																		✓		
Additional Examinations																		✓		
Concomitant Medication																		✓		
Adverse Event																		✓		
Serious Adverse Event																		✓		

Treatment Cycle Visit Test Items	Screening Period	C1		C2		C3	C4	C5	C6	C7	C8	C9	C10	C11	Withdrawal	28 Days after Withdrawal		Follow-up 1	Follow-up 2	
		V1 (-3W)	V2	V3	V4	V5	V6	V7	V8	V9	V10	V11	V12	V13	V14	Vn	Vn+1	V100	V101	V201
Summary of Study																		√		
Survival Follow-Up																				√

Note: (1) The results of ECOG PS, hematology, urinalysis, blood biochemistry, coagulation function, quality of life score, and ECG must be collected within 1 week before randomization.

- (2) a: Chest X-ray: If the chest CT has been performed during the screening period, chest X-ray is not required.
- (3) b: Serum AFP: Only detected at the end of Cycle 2 and Cycle 5; not strictly required after Cycle 5.
- (4) c: Urinalysis: Not required for female subjects during their menstrual period.
- (5) d: Pregnancy test: Additional pregnancy tests can be carried out during the treatment period if necessary.
- (6) e: Stool routine (occult blood): In the case of fecal occult blood (+) during the screening period, a gastroscopy is required; and additional fecal occult blood tests can be carried out during the treatment period if necessary.

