- (7) f: Echocardiography: Must be performed during the screening period. For clinically significant ECG abnormalities observed during the study period, an additional echocardiography examination is required.
- (8) g: ECG: The QTc interval must be indicated for 3 times, with about 5 min apart. ECG examination shall be carried out before drug administration during the screening period and then always after drug administration in each visit. For clinically significant ECG abnormalities, an additional echocardiography examination is required; if there are symptoms such as precordial pain and palpitations, the myocardial zymogram (creatinine kinase, lactate dehydrogenase) should be tested immediately. The examination should be carried out every two cycles after Cycle 3.
- (9) h: Quality of life score: Must be measured before the efficacy evaluation; and measured every two cycles after Cycle 3.
- (10) i: Imaging examination: Screening period: including CT or MRI of the chest and abdomen. Brain CT/MRI is required for clinically suspected metastases to the central nervous system. A bone scan is required for clinically suspected bone metastasis. Treatment period: The examination should be carried out in Cycles 2 and 3, and then every two cycles after Cycle 3.
- (11) i: Efficacy evaluation: The first efficacy evaluation is carried out at the end of Cycle 2; efficacy confirmation is carried out at 4 weeks after the first efficacy evaluation (i.e., at the end of Cycle 3). Afterwards, the efficacy evaluation is carried out every two cycles; For subjects who withdraw from the study due to unacceptable toxicity, the efficacy evaluation should be conducted upon withdrawal if the efficacy evaluation is not carried out within 4 weeks before withdrawal. Thereafter, the imaging examination is performed every 2 cycles until progressive disease.
- (12) Follow-up 1 (can be repeated for V101): The subjects who withdraw from the study due to unacceptable toxicity should be followed-up for tumor progression until the tumor progression is confirmed by imaging or the start of new anti-tumor treatment.
- (13) Follow-up 2 (can be repeated for V201): Survival follow-up, visit number from 201, 202, 203...

REGULATIONS FOR DOSE MODIFICATION

NCI Toxicity Grade	Regulations for Dose Modification	Regulations for Toxicity Recovery upon Re-Administration after Treatment Discontinuation	Regulations for Toxicity Recovery at the Beginning of Next Cycle

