4.5.4 Treatment cycle

Subjects who achieve complete response (CR), partial response (PR), and stable disease (SD) should continue treatment until PD, unacceptable toxicity, or subjects request to discontinue treatment.

Notes: For subjects with PD, treatment should be discontinued in principle. However, in view of the treatment characteristics of molecular targeted drugs, there are certain defects to adopt the evaluation method of cytotoxic chemotherapy. After receiving molecular targeted therapy, although the tumor of some subjects was enlarged, remarkable necrosis or denaturation was observed inside the tumor, and CT showed that the internal density of the tumor lesion decreased. It is generally considered to be beneficial to subjects under this circumstance. Therefore, it is specified in the study protocol that: if obvious necrosis or denaturation is observed in the tumor tissue, tumor-related symptoms are significantly improved or remained stable, the subject voluntarily continues the treatment, and continuing treatment may achieve

survival benefits as judged by the principal investigator, the subject can continue to receive the treatment until intolerance of toxicity or PD again, with strict observation.

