4.6 Efficacy Evaluation and Analysis

Efficacy evaluation should be performed every two cycles (this is based on calendar days and is not affected by treatment interruption), and the evaluation time is \pm 7 days at the end of the cycle (except for statutory holidays). CT or MRI examinations are required for evaluation. The radiographic technique should be consistent for all the tests of a subject, and all the images should be retained. If the efficacy reaches CR, PR or SD by imaging, the subject must be reexamined 4 weeks to confirm the evaluation.

In the case of imaging-confirmed PD, the subject should discontinue the treatment and then enter the follow-up period. Other anti-tumor treatments are prohibited before PD.

For subjects who withdraw from the trial due to unacceptable toxicity, the efficacy evaluation by imaging should be conducted upon withdrawal if the efficacy evaluation is not carried out within 4 weeks before withdrawal. Thereafter, the imaging examination is performed with the same frequency, i.e., every 2 cycles until PD or initiating other anti-tumor treatments to get the result of their radiographic PD.

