4.9 Survival Follow-Up

After the 28-day safety follow-up, the subject, his/her family members, or local physicians should be interviewed by telephone once a month to collect survival (date and cause of death) and post-treatment information (including received treatments) until death, lost to follow-up, or study termination by Hengrui. Each survival follow-up should be documented in the follow-up form in detail.

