9.2 Treatment Period

- Check the blood pressure once a week post-administration. If the blood pressure is abnormal, follow up with the blood pressure every day, and check the blood pressure three times a week for two cycles after the blood pressure returns to normal, and once a week thereafter.
- Within the first two cycles of administration, carry out the following examinations every two weeks (± 3 days, except for statutory holidays): hematology, urinalysis (not required for female subjects during their menstrual period), hepatic and renal function, and electrolytes. From Cycle 3, the examination is carried out once only at the end of each cycle (± 3 days, except for statutory holidays).
- Within the first three cycles of administration, a 12-Lead ECG is carried out at the end of each cycle (± 3 days, except for statutory holidays), and then carried out at the end of every two cycles (± 7 days, except for statutory holidays). Each examination is carried out after administration for 3 times with about 5 min apart and QTc interval indicated. If there are symptoms such as precordial pain and palpitations, the myocardial zymogram (creatinine kinase, lactate dehydrogenase) should be tested immediately, and ECG should be performed at any time. For clinically significant ECG abnormalities, echocardiography (LVEF) should be performed.
- Physical examination, vital signs, PS score, and coagulation function tests are performed every cycle (± 3 days, except for statutory holidays).
- CT or MRI examination and objective efficacy evaluation of tumor are performed once at the end of every two cycles (± 7 days, except for statutory holidays). If the efficacy reaches CR, PR or SD, the subject must be reexamined 4 weeks after the first evaluation.

Note: For subjects who withdraw from the trial due to unacceptable toxicity, the efficacy evaluation should be conducted upon withdrawal if the efficacy evaluation is not carried out within 4 weeks before withdrawal. Thereafter, the imaging examination is performed at the same frequency, i.e., every 2 cycles until PD or use of other anti-tumor treatments. The radiographic evidence of PD of these subjects must be obtained.

- The quality of life score must be evaluated before each objective efficacy evaluation of tumor.
- Serum AFP is tested once at the end of Cycle 2 (± 7 days, except for statutory holidays) and at the end of Cycle 5 (± 7 days, except for statutory holidays). There is no strict requirement after Cycle 5.

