- Based on the FAS, the changes of the total quality of life scores from baseline between the two groups for each time point are compared by analysis of variance model (ANOVA). The changes from baseline in global health status, total quality of life score, and score of EORTC QLQ-HCC18 at each scale for each time point are compared by Wilcoxon rank-sum test between groups.

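### Quality of life is tested between arms visit by visit, with no repeated-measures model and no missing-data rule in the SAP, although patients stop being scored at different rates in the two arms

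*SAP*

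**What the plan says.** **Analysis.** SAP 7.3.2 compares change from baseline between arms on the FAS, one time point at a time. Total score is tested by ANOVA. Global health status, total score (a second time) and the liver-module scales are tested by rank-sum: "score of EORTC QLQ-HCC18 at each scale for each time point are compared by Wilcoxon rank-sum test between groups". No longitudinal model, handling of death or sensitivity analysis is given for QoL.

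**Missing data.** SAP 7.1.3 says that missing laboratory, ECG and vital-sign values are not imputed; QoL is not named. Protocol 12.2 permits last observation carried forward (LOCF) in its FAS definition. The FAS definition in SAP 6.1 does not repeat this.

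**Collection.** The footnote to the Schedule of Activities says of QoL: "Must be measured before the efficacy evaluation; and measured every two cycles after Cycle 3". Protocol 9.2 agrees: "The quality of life score must be evaluated before each objective efficacy evaluation of tumor". Protocol 10.2 gives the times as pre-treatment, the ends of Cycles 2 and 3, then every two cycles. Read by column position, the Schedule's QoL row also has ticks at withdrawal and 28 days after it, and none at Follow-up 1 or Follow-up 2. The text of the 28-day visit (Protocol 4.7 and 9.3.1) does not list QoL.

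**Leaving treatment.** Protocol 4.6: "In the case of imaging-confirmed PD, the subject should discontinue the treatment and then enter the follow-up period". Protocol 4.5.4 makes an exception for selected subjects: "the subject can continue to receive the treatment until intolerance of toxicity or PD again". After the 28-day visit, patients or contacts are "interviewed by telephone once a month to collect survival (date and cause of death) and post-treatment information" (Protocol 4.9).

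**The concern.** Randomisation protects a comparison of all randomised patients. A visit-wise test of observed scores compares only those still attending. If placebo patients leave sooner, and those who leave tend to have worse QoL, the placebo patients left at a late visit are a smaller and fitter share of their arm. The test can then show a difference when treatment has no effect on QoL, and the report would present it as a treatment effect. If LOCF were applied instead, the groups would not shrink, but scores of different ages would be carried past progression and death. The SAP does not say which of the two will be done.

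**Working it through.** The documents give no figure for QoL power, completion or missingness, so there is no plan figure to reproduce.

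**Inputs from the documents**
- Median OS 8.5 v 6 months (Protocol 4.3, SAP 2.4).
- 390 patients at 2:1 (Protocol 4.1), so 260 v 130.
- Median time to progression 3.3 months at 750 mg in the phase II HCC trial (Protocol 1.5.7), used as a proxy for time on apatinib.

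**Assumptions, not in the documents**
- Placebo median time on treatment 1.5 to 2.5 months.
- Exponential times.
- SD of QoL change 20 points.
- Correlation ρ of 0.3 to 0.5 between QoL change and time on treatment, on a latent normal scale.

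**Step 1: who has a score.** The first scheduled post-baseline scan is at the end of Cycle 2, and QoL precedes it. Scheduled imaging therefore removes nobody before the Cycle 2 score. A patient whose Cycle 5 scan shows progression already has a Cycle 5 score. So Cycle 3 depends on staying past the Cycle 2 scan, Cycle 5 on the Cycle 3 scan, and Cycle 7 on the Cycle 5 scan.

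**Step 2: deaths alone.** Share alive = 2^(−t/median), with t in months (days/30.4375).
- Day 56: 2^(−1.84/8.5) = 86% v 2^(−1.84/6) = 81%.
- Day 140: 2^(−4.60/8.5) = 69% v 2^(−4.60/6) = 59%.

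The plan's own survival assumptions already imply unequal loss.

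**Step 3: share remaining to be scored.** Share = 2^(−t/median), with t at the previous scan.

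| Score at | Previous scan | Apatinib (3.3) | Placebo (1.5 to 2.5) | Patients |
|---|---|---|---|---|
| Cycle 3 | day 56, 1.84 mo | 68% | 43-60% | 177 v 56-78 |
| Cycle 5 | day 84, 2.76 mo | 56% | 28-47% | 146 v 36-60 |
| Cycle 7 | day 140, 4.60 mo | 38% | 12-28% | 99 v 16-36 |

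Losses between the previous scan and the score are ignored, so these shares are slightly high.

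**Step 4: bias with no true effect.** If the top fraction p of a standard normal remains, its mean is m(p) = φ(z_p)/p, where z_p is the value exceeded with probability p. Bias = 20 × ρ × [m(p placebo) − m(p apatinib)], in points against apatinib.
- Cycle 2, deaths only: m = 0.258 v 0.337. 20 × 0.3 × 0.079 = 0.5; 20 × 0.5 × 0.079 = 0.8.
- Cycle 3: m = 0.527 v 0.643 to 0.918. 6 × 0.116 = 0.7; 10 × 0.391 = 3.9.
- Cycle 5: m = 0.704 v 0.854 to 1.204. 6 × 0.150 = 0.9; 10 × 0.500 = 5.0.
- Cycle 7: m = 1.001 v 1.204 to 1.670. 6 × 0.203 = 1.2; 10 × 0.669 = 6.7.

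**Step 5: false-positive rate.** A simulated rank-sum test (2,000 trials per setting, no true effect, same correlations) was run with placebo medians of 1.44 to 2.33 months. At 56% v 26-44% retained, which matches the Cycle 5 score, it rejected in 6% to 33% of trials. At 38% v 10-25%, which matches Cycle 7, it rejected in 7% to 27%. With equal retention or zero correlation, rejection was about 5% and the bias about zero.

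**The case against.** Several stronger readings are tempting, and the documents do not support them.

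- *Only progression-free patients have a score at Cycle 5 or 7.* Not so. QoL precedes the scan, and Protocol 4.5.4 lets selected patients continue after progression.
- *The SAP discards the withdrawal and 28-day scores.* It does not exclude them. It refers to each time point and does not say how these scores enter.
- *QoL collection clearly ends with treatment.* The Schedule also has ticks at withdrawal and 28 days later. Imaging continues after withdrawal for toxicity, and Protocol 9.2 ties QoL to each tumour evaluation, yet the Follow-up 1 column has no QoL tick. The documents are unclear here.
- *The bias must work against apatinib.* This is an inference. Toxicity stops would remove apatinib patients with poor scores and push the other way. In phase II, 72.6% of the 750 mg arm had Grade III-V events (Protocol 1.5.7), and 3 patients in that arm withdrew for adverse events within one cycle (Protocol 4.5.2).

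It can also be said that LOCF, if applied, keeps the groups whole. That removes this mechanism but substitutes stale scores, and the SAP is silent on it. SAP 7.1 and 7.1.3 already call for counts of non-missing and missing values, but not against the number alive.

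What stands is that the size rests on assumed placebo retention, SD and correlation, and the direction is likely but not certain. Unequal loss is not mere conjecture: it follows from the plan's own OS medians. The PFS comparisons that the protocol cites point the same way: 5.5 v 2.8 months for another drug in HCC (1.2.2), and 96-110 v 42 days for apatinib in gastric cancer (1.5.5).

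**Conclusion.** The point holds as a modest improvement to a secondary endpoint. The SAP tests QoL visit by visit among patients whose continued attendance depends on outcome, and gives no missing-data rule for it. Selection is slight at Cycle 2 and increases later. The estimated observed-case bias of 0.9-5.0 points at Cycle 5 and 1.2-6.7 at Cycle 7 is conditional on the assumptions listed and shrinks to about zero if retention is equal or unrelated to QoL. The OS analysis, on which the superiority claim rests, is not affected.

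**What to change.** In SAP 7.3.2:
1. Make the main QoL comparison a mixed model for repeated measures by time since randomisation, including the withdrawal and 28-day scores already on the Schedule, and state how these are placed in time.
2. State that LOCF is not used for QoL, which settles the open sentence in Protocol 12.2.
3. Report number scored over number alive, by arm and visit.
4. Make visit-wise comparisons after Cycle 3 descriptive.

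In the protocol, reconcile 4.7 and 9.3.1, which omit QoL, with the Schedule, which has it at 28 days.

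The cost is SAP wording and one line in each protocol section, with no new visits. The model assumes that scores are missing at random given earlier ones. Death and progression strain that assumption, although the withdrawal and 28-day scores help. Late visits lose their P values. The Cycle 2 and 3 comparisons still carry a smaller bias, so the model and the completion counts matter more than the exact cut-off.

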## 7.4 Safety Evaluation

### 7.4.1 Adverse events

AEs are encoded according to the current MedDRA 21.0 and then processed in statistical analysis.

The incidences of AEs, treatment-related adverse events (TRAEs), AEs leading to drug interruption, dose reduction, and drug discontinuation, and SAEs are summarized. If multiple AEs occurred in the same subject, the number of subject is counted as one when calculating the incidence; if a subject experiences multiple times of a same AE, the number of subject is counted as one when calculating the incidence of the AE.

AEs are summarized in the frequency table based on SOC and PT. The incidence is calculated based on SOC and symptom/sign (the number of cases is counted as number of subjects who have experienced at least one AE).

Severity of AEs and treatment-related adverse events: If a subject experiences multiple times of the same AE, the most severe one will be used in the analysis of the severity of the AE.

A list of cases of AEs and SAEs is provided.

The median time to the onset of the first event is calculated for the adverse events of special interest (AESIs). AESIs include hypertension, proteinuria, hand-and-foot syndrome, hemorrhage, electrocardiogram QT prolonged, and white blood cell count decreased. The specific classification definitions are shown in Appendix 2.

Time to the onset of first event (days) = onset date of first event – date of the first dose + 1

In addition, for the comparisons of the incidences of AEs between the treatment group and the control group, the Fisher's exact method may be used to calculate the P value, which is only used for clinical reference, rather than the deduction of statistical significance.

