### 2.4 Sample Size

In this trial, placebo is used as a control and a superiority test is performed between the two groups.

Assuming the median OS for the placebo group and the apatinib group is 6 months and 8.5 months, respectively, according to FAS analysis results for a phase II clinical trial and relevant literature reports, assuming the two-sided  $\alpha = 0.05$  and 80% power, with 2:1 randomization (treatment vs placebo), the lost to follow-up rate for each group is 15%, and assuming the accrual period is 12 months, and the duration of study period is 36 months, 331 subjects is required to be enrolled (222 subjects in the treatment group, 109 subjects in the placebo group) according to the calculation formula of the Log-rank test for the OS comparison between two groups (calculated by the PASS software), see Table 1 below. Considering dropout and other factors, this trial plans to enroll 360 patients, including 240 for the treatment group and 120 for the placebo group. According to the resolution of scientific committee on 31 Oct. 2016, 390 subjects are planned to be enrolled (see the Resolution of Scientific Committee on 31 Oct., 2016).

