### 4.1 Adverse Events

AEs, treatment-related adverse events (TRAEs), and SAEs that have occurred during the study period.

An AE refers to any untoward medical occurrence in a clinical investigation subject and which does not necessarily have a causal relationship with the treatment. AEs include but are not limited to: laboratory abnormalities; clinically significant symptoms and signs; allergies;

According to the needs of management, safety monitoring (reporting of AEs or SAEs) should be performed from the signing of the informed consent form by the subject to 28 days after the last dose.

Treatment-related AEs (TRAEs): All toxicities and unintentional reactions to a drug associated with any dose should be considered as Treatment-related AEs (TRAEs). Treatment-related AE means that a potential causal relationship between the drug and AE is at least reasonable, which means that the relationship cannot be excluded. The potential relationship between an AE and the investigational drug is assessed with 5 grades of causality: definitely related, probably related, possibly related, unlikely related, and not related. Events that are assessed to be "definitely related", "probably related", and "possibly related" are considered related to the investigational drug. When calculating the incidence of Treatment-related AEs, the total number of these three categories is used as the numerator and the total number of subjects in safety set is used as the denominator.

A SAE refers to a medical occurrence during the clinical trial that results in hospitalization, prolonged hospitalization, disability, incapacity, life threatening events or death, or congenital malformation. The following unexpected medical events are included:

- Events resulting in death;

- Life-threatening events (defined as events where the subject is at immediate risk of death at the time of the onset);
- Events resulting in hospitalization or prolonged hospitalization;
- Events resulting in permanent or serious disability/incapacity;
- Congenital anomalies or birth defects;
- Overdose;
- Pregnancy during the clinical trial.

Criteria for other SAEs specified in the protocol:

- Cardiac insufficiency — defined as any symptom or sign of reduced LVEF (NCI CTCAE Grade 3), or LVEF reduced by  $\geq 20\%$  from baseline and below the lower limit of normal (or reduced to  $< 50\%$ ).

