#### **7.1.2 Hypothesis test**

The primary efficacy endpoint for this trial is OS.

The log-rank test is used for the comparison between the investigational drug group and control group:

Hypothesis:

$H_0$ : The survival function of the apatinib group is the same as that of the placebo group;

$H_1$ : The survival function of the apatinib group is different from that of the placebo group.

$\alpha$  level: 0.05 (two-sided).

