#### **7.4.2 Drug exposure and dose modification**

The drug exposure in the two groups is described using mean, standard deviation, maximum, minimum, and median.

The treatment interruption and dose modification during the trial are summarized.

The duration of drug exposure, actual dose intensity, and relative dose intensity of apatinib and placebo are summarized using mean, standard deviation, median, maximum, and minimum.

The specific definition rules of derived variables for the study drugs apatinib and placebo are shown in Appendix 3.

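### SAP 7.4.1 gives adverse event incidence per subject only; for events that accrue over time, the arm contrast is confounded with observation time if the arms stop drug at different times

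*SAP*

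**What the plan says.** - **Counting.** SAP 7.4.1 counts a subject once per event when calculating incidence. Where a denominator is stated (treatment-related AEs in SAP 4.1, adverse drug reactions in Protocol 11.2), it is the number of subjects in the safety set. For other AE classes the same denominator is the natural reading, but it is not written out.
- **Window.** Under SAP 4.1, AEs and SAEs are collected "from the signing of the informed consent form by the subject to 28 days after the last dose". Protocol 11.1.3 closes the window earlier for events other than death once a new anti-tumor treatment begins. Protocol 11.3 keeps it open later only for SAEs suspected to be drug-related.
- **Treatment length.** Under Protocol 4.5.4, subjects with response or stable disease "should continue treatment until PD, unacceptable toxicity, or subjects request to discontinue treatment". The same section allows some subjects to continue beyond progression.
- **Comparison.** SAP 7.4.1 permits Fisher's exact test "for the comparisons of the incidences of AEs between the treatment group and the control group", and says the P value is for clinical reference and not for concluding statistical significance. Protocol 12.3 calls the safety analysis mainly descriptive and has Fisher's test if necessary, without the reference-only qualifier.
- **Exposure.** SAP 7.4.2 states: "The duration of drug exposure, actual dose intensity, and relative dose intensity of apatinib and placebo are summarized". Appendix 3 of the SAP defines the duration. Neither feeds into an AE rate.
- **Timing.** SAP 7.4.1 gives the median time to first event for the six AESIs only, with no censoring rule.

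**The concern.** Safety is part of the study objective. Observation time for AEs is largely set by when a subject stops drug, which is tied to progression, and apatinib is meant to delay progression. Bilirubin rise, transaminase rise, abdominal pain and SAEs can all occur in advanced HCC without any drug effect. For events of that kind, a crude percentage on the longer-observed arm mixes toxicity with time at risk. A reader of the main AE tables could take longer observation for excess toxicity. If toxicity withdrawals shortened exposure on apatinib, the crude table would err the other way and understate toxicity.

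**Working it through.** **The plan's own figures.** Neither document gives a power or precision figure for AE comparisons. The only design figure with full inputs is the OS sample size of 331. With "Assuming the median OS for the placebo group and the apatinib group is 6 months and 8.5 months, respectively", two-sided 0.05 and 80% power at 2:1, Schoenfeld's formula gives 292 deaths. With exponential survival, 12 months' accrual, 36 months in total and 15% loss spread over 24 months, that becomes about 332 subjects. The OS design therefore reproduces, and it is not affected by this point.

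**Inputs.**
- SAE incidence on 750 mg in the phase II HCC trial: 12/51 = 23.5% (Protocol 1.5.7, Table 5).
- Post-treatment tail: 28 days (SAP 4.1).
- Median time on drug by arm is not stated. Progression figures quoted in the documents stand in for it, as assumptions:
  - 3.3 months, phase II HCC TTP at 750 mg (Protocol 1.5.7)
  - 5.5 and 2.8 months, cited sorafenib trial (Protocol 1.2.2)
  - 110 and 42 days, gastric phase II PFS, 850 mg once daily vs placebo (Protocol 1.5.5)
  - the planned OS ratio applied to time on drug: 3.3 × 6/8.5 = 2.33 months

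**Formula.** Take a constant hazard h per day, the same in both arms, and exponential time on drug with mean μ = median/ln 2, followed by 28 days. Then

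P(at least one event) = 1 − exp(−28h)/(1 + hμ).

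Solve for the h that gives 23.5% on apatinib, then apply it to the placebo μ. One month is 30.44 days.

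*Smallest gap, 3.3 vs 2.8 months.* μ = 144.9 and 123.0 days; h = 0.001700. Apatinib: 1 − 0.9535/1.2464 = 23.5%. Placebo: 1 − 0.9535/1.2091 = 21.1%.

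*Largest gap, 110 vs 42 days.* μ = 158.7 and 60.6 days; h = 0.001579. Apatinib: 1 − 0.9567/1.2506 = 23.5%. Placebo: 1 − 0.9567/1.0957 = 12.7%.

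| Assumed medians, apatinib vs placebo | Mean window (days) | Crude SAE incidence | Ratio |
|---|---|---|---|
| 3.3 vs 2.8 months | 173 vs 151 | 23.5% vs 21.1% | 1.11 |
| 3.3 vs 2.33 months | 173 vs 130 | 23.5% vs 18.8% | 1.25 |
| 5.5 vs 2.8 months | 270 vs 151 | 23.5% vs 14.7% | 1.60 |
| 110 vs 42 days | 187 vs 89 | 23.5% vs 12.7% | 1.85 |

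The true rate ratio is 1.00 in every row.

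**Other event rates.** With an apatinib median of 3.3 months, placebo medians from 2.8 down to 1.26 months (3.3 × 42/110) and hazards of 0.05 to 0.4 per month, the spurious difference is 2 to 18 percentage points and the ratio 1.04 to 1.84. With equal exposure (3.3 vs 3.3 months, 0.1 per month) both arms show 38.2%.

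**What person-time does to early events.** Suppose 30% vs 20% of subjects have the event, spread evenly over the first 28 days, so the true risk ratio is 1.5. In the 110 vs 42 day case, person-time per subject is 0.30 × 14 + 0.70 × 186.7 = 134.9 days on apatinib and 0.20 × 14 + 0.80 × 88.6 = 73.7 days on placebo. The rate ratio is (0.30/134.9)/(0.20/73.7) = 0.82. At 3.3 vs 2.8 months it is 1.48. Person-time rates can therefore hide a real early excess when exposure differs strongly.

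**The case against.** The strongest reply is that this is a descriptive table. A reader might infer that the plan will declare toxicity significant from a biased test. In simulation at 260 vs 130 subjects, Fisher's test gives P ≤ 0.05 in about 8% of trials in the smallest-gap case and about 70% in the largest. The documents do not support that inference: the SAP makes the test optional and says its P value carries no conclusion about significance. What remains is that the incidence contrast itself is distorted with or without a P value.

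A second tempting reading is that nothing in the report would reveal the problem. That also goes too far. Exposure is summarized by arm, AESIs have an onset time, and AE and SAE cases are listed. These show that a gap exists, but they do not let a reader adjust a given AE row.

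Third, the size depends on borrowed medians. The largest case comes from another tumour and another dose. The one built on the HCC 750 mg figure against the cited placebo figure is small. Protocol 4.5.2 reports withdrawals for adverse events within one cycle, so apatinib subjects need not be the longer-treated ones. This stands, and it is why only a range can be given.

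Fourth, many events come early. In phase I, hand-foot-skin reaction and hypertension each reached 47.4% in cycle 1 (Protocol 1.5.1). Crude incidence handles such events reasonably well. An SAE that marks the end of treatment is also comparable per subject: if it fell at the close of the window with equal risk in both arms, a person-time ratio in the largest case would be about 88.6/186.7 = 0.47, falsely favouring apatinib. This stands too, and it rules out replacing crude incidence with person-time rates.

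**Conclusion.** The point holds in conditional form. The plan reports AE incidence per subject over a window whose length depends on when drug stops, and no planned analysis adjusts for that. For events that accrue over time, equal hazards would appear as an excess on whichever arm is treated longer. Under the stated assumptions, the spurious SAE ratio lies between 1.11 and 1.85 (2.4 to 10.8 percentage points). The distortion is smaller for early-onset events and absent with equal exposure. These sizes rest on a constant hazard equal in both arms, exponential time on drug, and progression medians standing in for unstated treatment durations. The full 28-day tail is also assumed; an early switch to new therapy would shorten it.

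The consequence is limited to descriptive safety interpretation. The primary OS test and the sample size are untouched. The documents support neither a claim that apatinib will certainly be observed longer nor one that person-time rates should decide the safety conclusion.

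**What to change.** In SAP 7.4.1, keep the crude incidences and add beside them, for any AE, Grade ≥ 3 AE, SAE, treatment-related AE and each AESI:

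1. Exposure-adjusted incidence with rate ratio and 95% CI: subjects with a first event divided by person-time. Person-time runs from first dose to the first event or to the earliest of last dose + 28 days, start of new anti-tumor treatment (for non-fatal events, matching Protocol 11.1.3), death, or data cut-off. Count numerator events over the same interval.
2. Cumulative incidence of first event over time by arm, with the same end of observation and death as a competing event.

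State that the three measures are read together and that none governs interpretation. The named downside is that person-time rates assume a roughly constant hazard and can dilute early-onset toxicity on the longer-treated arm. The crude table and the cumulative incidence curves guard against that.

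The cost is SAP wording, one extra table and a set of curves, from dates already collected. No new follow-up is needed, and nothing changes in the OS analysis.
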